5.2 Elbasvir/grazoprevir prior and concomitant medications

Elbasvir/grazoprevir is contraindicated with organic anion transporting polypeptides 1B1/3 (OATP1B1/3) inhibitors, strong inducers of cytochrome P450 3A (CYP3A), and efavirenz. See Table 2 for details.

Table 2: Drugs that are contraindicated with elbasvir/grazoprevir

Drug Class	Drug(s) within Class that are Contraindicated	Clinical Comment*
Anticonvulsants	Phenytoin Carbamazepine	May lead to loss of virologic response to elbasvir/grazoprevir due to significant decreases in elbasvir and grazoprevir plasma concentrations caused by strong CYP3A induction.
Antimycobacterials	Rifampin	May lead to loss of virologic response to elbasvir/grazoprevir due to significant decreases in elbasvir and grazoprevir plasma concentrations caused by strong CYP3A induction.
Herbal Products	St. John's Wort (Hypericum perforatum)	May lead to loss of virologic response to elbasvir/grazoprevir due to significant decreases in elbasvir and grazoprevir plasma concentrations caused by strong CYP3A induction.
HIV Medications	Efavirenz†	May lead to loss of virologic response to elbasvir/grazoprevir due to significant decreases in elbasvir and grazoprevir plasma concentrations caused by CYP3A induction.
HIV Medications	Atazanavir Darunavir Lopinavir Saquinavir Tipranavir	May increase the risk of ALT elevations due to a significant increase in grazoprevir plasma concentrations caused by OATP1B1/3 inhibition.
Immunosuppressants	Cyclosporine	May increase the risk of ALT elevations due to a significant increase in grazoprevir plasma concentrations caused by OATP1B1/3 inhibition.

*This table is not a comprehensive list of all drugs that inhibit OATP1B1/3 or strongly induce CYP3A.

†Efavirenz is included as a strong CYP3A inducer in this table, since co-administration reduced grazoprevir exposure by ≥80%.

Should any participant need to initiate treatment with an excluded concomitant medication during the study, the Medical Monitor, A/[name] must be consulted prior to the initiation of any excluded medication. In the event that an excluded medication is initiated prior to discussion with A/[name], she must be made aware of the use of the excluded medication as soon as possible. A/[name] contact details are listed on the cover of this protocol.

6. Study procedures

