Study procedures	
Refer to the Schedule of Assessments and Study Procedures (Section 6)

Statistics	
Primary Objective: To evaluate the proportion of patients with undetectable HCV RNA at 12 weeks post end of treatment (SVR12) following elbasvir/grazoprevir therapy among PWID with recent injecting drug use or receiving OST and chronic HCV genotype 1 or 4 infection and evaluate demographic and clinical predictors of non-response.
 
Assuming an overall SVR of 90% (135 of 150), the 95% confidence interval around this estimate will be 84.0% to 94.3%. This study will have robust power to examine the effect of treatment setting on SVR: e.g. 80% power to detect an odds ratio of 0.39 or 2.59 or more extreme (with alpha=0.05)

for a variable that is 50% prevalent.

Secondary Objective: Estimate incidence and predictors of HCV reinfection after successful elbasvir/grazoprevir.

Schedule of Assessments

Assessment / Procedure	Screen	Baseline	W4	Safety	Study Treatment (weeks)	Follow-up (weeks)							
						24	36	48	60	84	108	132	156
Study weeks	-6 to 0	0	4	8	12 (ETR)	24 (SVR12)	36 (FU1)	48 (FU2)	60 (FU3)	84 (FU4)	108 (FU5)	132 (FU6)	156 (FU7)
Study Days	-42 to 0	0	28	56	84	168	252	336	420	588	756	924	1092
Visit Window (Days)			+/- 7	+/- 7	+/- 14	+/- 14	+/- 14	+/- 14	+/- 14	+/- 14	+/- 14	+/- 14	+/- 14
Informed consent, medical history	x												
Vital signs & physical measurements	x	x											
HCV-RNA testing (Local Laboratory)	x ^a		x ^a		x	x	x ^d						
HCV genotyping (Local Laboratory)	x												
Behavioural survey	x												
Abbreviated behavioural survey		x			x	x	x	x	x	x	x	x	x
Adherence survey and pill count			x	x	x								
Health outcomes survey (EQ-5D)	x				x	x							
Liver function tests/ Full blood count/ Biochemistry	x	x		x ^c	x	x							
HIV & HBV serology	x												
Fibroscan	x												
Pregnancy Test	x	x	x	x	x	x ^f							
Serious Adverse Events		x	x	x	x	x ^e							
Concomitant medication	x	x			x								
Research Sample (10 mL EDTA plasma and Whole Blood)	x ^b	x ^b	x	x	x	x	x	x	x	x	x	x	x
HCV sequencing/resistance testing (tested at Central lab using 10ml of research sample)						x ^g							
Finger-stick point-of-care HCV RNA testing (sub-study sites only)	x	x	x			x	x	x	x	x	x	x	x

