6.1 Visits and Procedures

The following assessments must be conducted at study visits as per the schedule of assessments:

Vital signs & physical measurements	Sitting systolic and diastolic blood pressure, heart rate, body weight ^a , height ^a
Fibroscan	Within 12 months prior to screening
Biochemistry	Creatinine, glucose, sodium, chloride, and potassium
Liver Function Tests	ALT, AST, GGT, total bilirubin, albumin, alkaline phosphatase, total protein
Full Blood Count	Haemoglobin, haematocrit, White Blood Cells, platelets, neutrophils
HCV RNA	Must be quantitative at Screening (within 12 weeks prior to Screening) and Week 4
HCV Genotype	Within 12 weeks prior to screening
HBV Serology	Anti-HBc, HBsAg and Anti-HBs testing (within 6 months prior to Screening)
HIV Serology	HIV antibody (within 6 months prior to Screening)
HCG Pregnancy Test	For women of childbearing potential, a negative urine (or serum) HCG test at screening, baseline, weeks 4, 8, week 12 (ETR) and week 14 (home test allowed at week 14)
Questionnaires	Behavioural survey, abbreviated behavioural survey, adherence questionnaire and EQ-5D
Finger-stick point-of-care HCV RNA testing (POC)	At sub-study sites only

^a at screening only

The following assessments and procedures must be performed at each visit as specified below:

Initial screening period (Week -6 to Week 0)

- Informed consent
- Medical history
- Vital signs and physical measurements
- Quantitative HCV RNA and genotype (Local Laboratory)
- LFTs, FBC and biochemistry
- HIV & HBV serology
- Fibroscan
- Pregnancy test (females of child bearing potential only)
- Concomitant medication
- Study questionnaires (Behavioural and EQ-5D)
- Research specimen collection (EDTA plasma & whole blood)
- Finger-stick point-of-care HCV RNA testing (Sub-study sites only)

Baseline visit (Week 0)

- Vital signs and physical measurements
- LFTs, FBC and biochemistry
- Pregnancy test (females of child bearing potential only)
- Serious Adverse Events
- Concomitant medication
- Study questionnaires (Abbreviated Behavioural)
- Research specimen collection (EDTA plasma & whole blood)
- Finger-stick point-of-care HCV RNA testing (Sub-study sites only)

On-Treatment Visits

Week 4 (+/- 7 days)

- Quantitative HCV RNA (Local laboratory)
- Pregnancy test (females of child bearing potential only)
- Serious Adverse Events
- Research specimen collection (EDTA plasma)
- Study questionnaire (Adherence)
- Finger-stick point-of-care HCV RNA testing (Sub-study sites only)

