
Week 8 (+/- 7 days)

- LFTs – ALT only
- Pregnancy test (females of child bearing potential only)
- Serious Adverse Events
- Research specimen collection (EDTA plasma)
- Study questionnaire (Adherence)

End of Treatment (ETR) - Week 12 (+/-14 days)

- Qualitative HCV RNA (where available, otherwise quantitative), (Local laboratory)
- LFTs, FBC and biochemistry
- Pregnancy test (females of child bearing potential only)
- Serious Adverse Events
- Concomitant medication
- Study questionnaires (Abbreviated Behavioural, Adherence, and EQ-5D)
- Research specimen collection (EDTA plasma)

Post Treatment Follow-up Visits

Post Treatment Week 12 (SVR12) - Week 24 (+/- 14 days)

- Qualitative HCV RNA (Where available, otherwise quantitative) (Local laboratory)
- LFTs, FBC and biochemistry
- Pregnancy test (females of child bearing potential only) (at 14 days post end of treatment – home test allowed)
- Serious Adverse Events (up to week 16 (SVR4) only)
- Study questionnaires (Abbreviated Behavioural and EQ-5D)
- Research specimen collection (EDTA plasma)
- Finger-stick point-of-care HCV RNA testing (Sub-study sites only)

Post Treatment Weeks 36 (FU1), 48 (FU2), 60 (FU3), 84 (FU4), 108 (FU5), 132 (FU6) and 156 (FU7) (+/- 14 days)

- Qualitative HCV RNA (Where available, otherwise quantitative) (Local laboratory)
- Study questionnaires (Abbreviated Behavioural)
- Research specimen collection (EDTA plasma)
- Finger-stick point-of-care HCV RNA testing (Sub-study sites only)

If a patient has suspected viral relapse or HCV reinfection HCV RNA sequencing will be performed. No additional sample is required.

Monitoring of HBV reactivation

At screening, all patients will be tested for evidence of current (Hepatitis B surface antigen positive) and prior (anti-Hepatitis B core antibody positive) HBV infection before initiation of treatment. Patients with current HBV infection will be excluded. Patients with evidence of prior HBV infection only will be enrolled.

Patients with evidence of prior HBV infection will be monitored for HBV reactivation and hepatitis flare during HCV treatment and post-treatment follow-up. LFTs will be performed 4-weekly during treatment. In the setting of a clinically significant ALT elevation or symptoms and signs of acute hepatitis, HBV DNA testing will be performed to assess for reactivation. Appropriate management for HBV infection will be initiated by the site investigator as clinically indicated.

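### No listed concomitant-medication check at Weeks 4 or 8, so an excluded drug started unplanned on treatment has no scheduled medication review until about the end of the 84-day course

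*Combined protocol and SAP*

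**What the plan says.** Section 5.2 deals with a participant who needs a contraindicated drug after enrolment ("Should any participant need to initiate treatment with an excluded concomitant medication during the study"). The Medical Monitor is to be consulted first. If the drug has already been started, the Medical Monitor "must be made aware of the use of the excluded medication as soon as possible". The duty follows the event and is not tied to a visit.

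Table 2 in the same section gives the reasons. For the enzyme inducers: "May lead to loss of virologic response to elbasvir/grazoprevir due to significant decreases in elbasvir and grazoprevir plasma concentrations". For the transporter inhibitors: "May increase the risk of ALT elevations due to a significant increase in grazoprevir plasma concentrations".

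The Schedule of Assessments has a row headed "Concomitant medication", marked at Screening, Baseline and Week 12. The Week 4 and Week 8 columns are blank. The visit lists in Section 6.1 match: the item appears under Screening, Baseline and end of treatment, and not under Week 4 or Week 8.

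**The concern.** Site staff can tell the Medical Monitor about a new drug only once they know of it. The schedule does list an assessment that would tell them, but after Baseline it falls only at the end-of-treatment visit. By then the check can document an exposure, but on the nominal timetable no treatment days remain on which to stop the drug, change it or monitor more closely.

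At stake is early recognition, in an individual participant, of an interaction that the protocol itself says may cost the virologic response or raise ALT. The participants concerned are those who start something unplanned, for example a new prescription from an outside clinician or a herbal product bought without one. Table 2 states that it does not list every relevant drug, so neither the participant nor an outside prescriber can be relied on to recognise each one.

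**Working it through.** **Inputs.** Treatment lasts 12 weeks (Section 4), that is 12 × 7 = 84 days. Visit days and windows come from the Schedule of Assessments and Section 6.1: Baseline on Day 0; Week 4 on Day 28 ± 7, or 21 to 35; Week 8 on Day 56 ± 7, or 49 to 63; Week 12 on Day 84 ± 14, or 70 to 98.

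**Step 1: is the omission real?** The Schedule and the visit lists are separate parts of the protocol and agree on every visit from Screening to Week 12. It is therefore not an artefact of a damaged table.

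**Step 2: the present gap.** Listed checks fall on Day 0 and Day 84.
- Nominal gap: 84 − 0 = 84 days, which is 84/84 = 100% of the course.
- Week 12 at its earliest: 70 − 0 = 70 days, which is 70/84 = 83% of the course.
- Week 12 at its latest: Day 98, which is 98 − 84 = 14 days after the planned last dose.

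**Step 3: the gap with Weeks 4 and 8 added.**
- Nominal gaps: 28 − 0, 56 − 28 and 84 − 56, each 28 days.
- Longest first gap: 35 − 0 = 35 days.
- Longest middle gap: 63 − 21 = 42 days.
- Longest last gap, counting treatment days only: 84 − 49 = 35 days.

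The longest stretch on treatment without a listed check is thus 42 days (Day 21 to Day 63).

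**Step 4: what else could reveal a new drug between Baseline and Week 12?**

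| Control | Where | What it reaches | What it leaves open |
|---|---|---|---|
| Exclusions 1 and 2; inclusion 5b | Section 3 | Drugs taken or planned at entry; the ART regimen at entry | A start that was not planned |
| SAE review at Weeks 4 and 8 | 6.1, 7.1.2 | Events such as hospital admission | New drugs given for non-serious reasons (7.1.1 limits study reporting to SAEs) |
| Week 4 HCV RNA | 6.1 | Poor early response | Anything started after Week 4; no local HCV RNA is listed at Week 8 |
| Week 8 ALT for all | 6.1 | Liver signal from a transporter inhibitor | Inducers, where the stated risk is lost response |
| "LFTs will be performed 4-weekly during treatment" | 6.1, HBV monitoring | The same liver signal, more often | Applies to participants with prior HBV only |
| Adherence questionnaire and pill count | 5.1, 6.2 | Adherence to elbasvir/grazoprevir | Items are not reproduced, so any question on other drugs cannot be verified |
| Supervised or pharmacist dispensing | Section 8 | A contact at supply of study drug | Drugs obtained elsewhere |
| Trial participation noted in the medical record | 12.1 | Alerts clinicians who open that record | Prescribers who do not see it; non-prescribed products |

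None of these is described as asking about newly started drugs. The abbreviated behavioural survey is not scheduled at Weeks 4 or 8.

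**The case against.** The strongest reply is that light monitoring is deliberate. The drug is licensed, supplied through the PBS and used within its indication; non-serious events follow ordinary PBS reporting, and the protocol gives the same reason for having no DSMB. Participants attend in person at Weeks 4 and 8 with an SAE review, an adherence questionnaire and a pill count, and a competent clinician would probably ask about other medicines whether or not the form lists the question. Nothing in Section 5.2 says that the Schedule row exists to enforce it. All of this stands, and it is why the point is minor. It does not remove the gap: the item is already thought worth listing at three visits, and none of the other controls is stated to do its job.

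A second objection also stands in part. The primary duty in Section 5.2 is consultation before starting, and a question at a visit mainly serves the fallback of reporting afterwards. The benefit should be described in those terms.

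A reader might infer more than this, in three ways that the documents do not support:

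- *That Section 5.2 and the Schedule contradict each other.* They do not. The duty applies continuously, whatever is listed at a visit.
- *That SVR12 will be biased.* The documents give no rate at which participants start contraindicated drugs, so neither a number affected nor an effect on the endpoint can be derived.
- *That nobody will ask about medicines before Week 12.* The documents show only that no such check is listed.

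**Conclusion.** The point holds as an inexpensive improvement to on-treatment monitoring, for consideration rather than as a required correction. The only listed medication check after Baseline falls nominally on the last day of the course. At least 70 of the 84 treatment days pass before it, and all 84 do if the visit is on time or late.

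These figures measure the spacing of listed checks, not risk. They assume an 84-day course that starts on Day 0 and visits kept within their windows. The frequency of unplanned starts is unknown, the existing controls will catch some of them, and no stated sample size, estimate or analysis changes.

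**What to change.** Add an item such as *Concomitant medication (new, stopped or changed since last visit, with dates)* to the Week 4 and Week 8 lists in Section 6.1, and mark those two columns in the Schedule of Assessments. State that any excluded drug found there is referred to the Medical Monitor under Section 5.2.

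The cost is a few minutes and one short eCRF page at two visits that participants already attend, plus a minor protocol amendment. No extra visit, sample or staff is needed, and the analysis is untouched.

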6.1 Visits and Procedures

The following assessments must be conducted at study visits as per the schedule of assessments:

Vital signs & physical measurements	Sitting systolic and diastolic blood pressure, heart rate, body weight ^a , height ^a
Fibroscan	Within 12 months prior to screening
Biochemistry	Creatinine, glucose, sodium, chloride, and potassium
Liver Function Tests	ALT, AST, GGT, total bilirubin, albumin, alkaline phosphatase, total protein
Full Blood Count	Haemoglobin, haematocrit, White Blood Cells, platelets, neutrophils
HCV RNA	Must be quantitative at Screening (within 12 weeks prior to Screening) and Week 4
HCV Genotype	Within 12 weeks prior to screening
HBV Serology	Anti-HBc, HBsAg and Anti-HBs testing (within 6 months prior to Screening)
HIV Serology	HIV antibody (within 6 months prior to Screening)
HCG Pregnancy Test	For women of childbearing potential, a negative urine (or serum) HCG test at screening, baseline, weeks 4, 8, week 12 (ETR) and week 14 (home test allowed at week 14)
Questionnaires	Behavioural survey, abbreviated behavioural survey, adherence questionnaire and EQ-5D
Finger-stick point-of-care HCV RNA testing (POC)	At sub-study sites only

^a at screening only

The following assessments and procedures must be performed at each visit as specified below:

Initial screening period (Week -6 to Week 0)

- Informed consent
- Medical history
- Vital signs and physical measurements
- Quantitative HCV RNA and genotype (Local Laboratory)
- LFTs, FBC and biochemistry
- HIV & HBV serology
- Fibroscan
- Pregnancy test (females of child bearing potential only)
- Concomitant medication
- Study questionnaires (Behavioural and EQ-5D)
- Research specimen collection (EDTA plasma & whole blood)
- Finger-stick point-of-care HCV RNA testing (Sub-study sites only)

Baseline visit (Week 0)

- Vital signs and physical measurements
- LFTs, FBC and biochemistry
- Pregnancy test (females of child bearing potential only)
- Serious Adverse Events
- Concomitant medication
- Study questionnaires (Abbreviated Behavioural)
- Research specimen collection (EDTA plasma & whole blood)
- Finger-stick point-of-care HCV RNA testing (Sub-study sites only)

On-Treatment Visits

Week 4 (+/- 7 days)

- Quantitative HCV RNA (Local laboratory)
- Pregnancy test (females of child bearing potential only)
- Serious Adverse Events
- Research specimen collection (EDTA plasma)
- Study questionnaire (Adherence)
- Finger-stick point-of-care HCV RNA testing (Sub-study sites only)

Week 8 (+/- 7 days)

- LFTs – ALT only
- Pregnancy test (females of child bearing potential only)
- Serious Adverse Events
- Research specimen collection (EDTA plasma)
- Study questionnaire (Adherence)

End of Treatment (ETR) - Week 12 (+/-14 days)

- Qualitative HCV RNA (where available, otherwise quantitative), (Local laboratory)
- LFTs, FBC and biochemistry
- Pregnancy test (females of child bearing potential only)
- Serious Adverse Events
- Concomitant medication
- Study questionnaires (Abbreviated Behavioural, Adherence, and EQ-5D)
- Research specimen collection (EDTA plasma)

Post Treatment Follow-up Visits

Post Treatment Week 12 (SVR12) - Week 24 (+/- 14 days)

- Qualitative HCV RNA (Where available, otherwise quantitative) (Local laboratory)
- LFTs, FBC and biochemistry
- Pregnancy test (females of child bearing potential only) (at 14 days post end of treatment – home test allowed)
- Serious Adverse Events (up to week 16 (SVR4) only)
- Study questionnaires (Abbreviated Behavioural and EQ-5D)
- Research specimen collection (EDTA plasma)
- Finger-stick point-of-care HCV RNA testing (Sub-study sites only)

Post Treatment Weeks 36 (FU1), 48 (FU2), 60 (FU3), 84 (FU4), 108 (FU5), 132 (FU6) and 156 (FU7) (+/- 14 days)

- Qualitative HCV RNA (Where available, otherwise quantitative) (Local laboratory)
- Study questionnaires (Abbreviated Behavioural)
- Research specimen collection (EDTA plasma)
- Finger-stick point-of-care HCV RNA testing (Sub-study sites only)

If a patient has suspected viral relapse or HCV reinfection HCV RNA sequencing will be performed. No additional sample is required.

Monitoring of HBV reactivation

At screening, all patients will be tested for evidence of current (Hepatitis B surface antigen positive) and prior (anti-Hepatitis B core antibody positive) HBV infection before initiation of treatment. Patients with current HBV infection will be excluded. Patients with evidence of prior HBV infection only will be enrolled.

Patients with evidence of prior HBV infection will be monitored for HBV reactivation and hepatitis flare during HCV treatment and post-treatment follow-up. LFTs will be performed 4-weekly during treatment. In the setting of a clinically significant ALT elevation or symptoms and signs of acute hepatitis, HBV DNA testing will be performed to assess for reactivation. Appropriate management for HBV infection will be initiated by the site investigator as clinically indicated.

Sites should advise patients of the risk of HBV reactivation and instruct patients on the signs and symptoms of reactivation (such as lethargy, nausea, jaundice). Patients should be encouraged to report any signs or symptoms.

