^a must be quantitative HCV RNA, ^b 4ml whole Blood and 20mL EDTA at Screening and Baseline only, ^c ALT only, ^d as per standard of care, ^e to week 16 only, ^f at 14 days post end of treatment (home test allowed) ^g To evaluate the prevalence of resistance associated substitutions and for relapse or reinfection as needed

1. Background and rationale

People who inject drugs (PWID) account for the majority of new (80%) and existing (60%) cases of HCV in high-income countries^{1, 2}. Development of chronic HCV infection may lead to progressive hepatic fibrosis, cirrhosis, and complications of liver failure or hepatocellular carcinoma³. The ageing cohort of PWID populations means that liver disease-related mortality is increasing⁴⁻⁷. However, treatment can attenuate HCV-related disease consequences, including all-cause mortality⁸. HCV transmission also continues to occur among PWID⁹. Estimated HCV incidence among PWID ranges from 5-45% per annum¹⁰. The risk of HCV infection is highest among recent initiates into injecting drug use. Harm reduction strategies, such as needle syringe programs (NSP) and opioid substitution treatment (OST) have been successful for HIV prevention among PWID, but have been less effective for HCV prevention¹¹⁻¹⁵. In many countries, low coverage of NSP and OST further hinders HCV prevention efforts¹⁶. Given that HCV transmission continues to occur among PWID and there is no HCV vaccine, strategies to achieve HCV elimination among PWID must be explored.

Data from mathematical modelling suggests that substantial reductions in HCV prevalence and incidence could be achieved among PWID with modest increases in treatment uptake with interferon-free HCV regimens¹⁷. Given the potential prevention benefits, HCV treatment among PWID is also cost-effective^{18, 19}. In fact, combining interferon-free HCV therapies with high coverage OST and NSP may lead to even greater reductions in HCV prevalence²⁰. As such, combination prevention strategies including “HCV Treatment as Prevention”, OST and NSP are critical for achieving reductions in HCV prevalence/transmission to very low levels¹⁸. Targeted treatment to those at risk of transmission could be used as an HCV “Treatment as Prevention” strategy to reduce onward transmission.

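### For participants with prior HBV infection, the 4-weekly liver tests stated in Section 6.1 are absent from the Week 4 visit list and the Schedule, and Week 8 has ALT only

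*Combined protocol and SAP*

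**What the plan says.** The HBV reactivation text in Section 6.1 excludes people with current HBV infection and enrols those with evidence of prior infection only. For the latter it states: "Patients with evidence of prior HBV infection will be monitored for HBV reactivation and hepatitis flare during HCV treatment and post-treatment follow-up". The next sentence gives the frequency: "LFTs will be performed 4-weekly during treatment". It then sets out what leads to further testing: "In the setting of a clinically significant ALT elevation or symptoms and signs of acute hepatitis, HBV DNA testing will be performed".

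The same section defines Liver Function Tests as "ALT, AST, GGT, total bilirubin, albumin, alkaline phosphatase, total protein", which is seven analytes. The abbreviations list (Section 19) gives the same seven.

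The visit-by-visit lists in Section 6.1 are introduced with "The following assessments and procedures must be performed at each visit as specified below". On treatment, they contain:

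- **Week 4:** quantitative HCV RNA, pregnancy test, serious adverse events, research plasma, adherence questionnaire and the finger-stick test. There is no LFT or ALT.
- **Week 8:** LFTs restricted to ALT.
- **Week 12 (end of treatment):** full LFTs, with blood count and biochemistry.

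In the Schedule of Assessments, the row "Liver function tests/ Full blood count/ Biochemistry" is marked at screening, Baseline, Week 8, Week 12 and Week 24. Week 4 is blank, and footnote c restricts Week 8 to ALT.

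**The concern.** The narrative text and the operational text give different on-treatment liver tests for the same people. The visit lists are worded as mandatory, and the synopsis refers readers to the Schedule and Section 6 for study procedures, so a site may well work from the lists or the Schedule alone. Such a site would do no liver test at Week 4 in a participant with prior HBV infection.

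This matters because HBV DNA is not tested routinely. It is tested after a clinically significant ALT elevation or after symptoms and signs of acute hepatitis. If no ALT is scheduled, only the clinical trigger remains, unless someone orders an unscheduled test. Reactivation that shows first as a rise in ALT without symptoms could go unseen until Week 8.

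There is also a question of meaning at Week 8. Under the protocol's own definition, an ALT alone is not the LFT panel that the HBV paragraph appears to call for.

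**Working it through.** The plan gives no figure to reproduce here. The check compares the stated frequency with the listed tests and then measures the gap in days.

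**Inputs**

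- Stated frequency: 4-weekly during treatment, an interval of 28 days (Section 6.1, HBV reactivation).
- Treatment duration: 12 weeks, 84 days (Sections 4 and 5).
- Visit days: Baseline 0, Week 4 = 28, Week 8 = 56, Week 12 = 84 (Schedule of Assessments).
- Window: +/- 7 days at Weeks 4 and 8 (Section 6.1 and Schedule).
- LFT panel: seven analytes (Section 6.1).

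**Step 1. Stated against listed.** Counting from Baseline, 4-weekly over 12 weeks gives 12/4 = 3 points.

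| Point | HBV paragraph | Section 6.1 visit list | Schedule row |
|---|---|---|---|
| Week 4 | LFTs | none | blank |
| Week 8 | LFTs | ALT only | marked, ALT only |
| Week 12 | LFTs | full LFTs | marked |

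ALT is scheduled at 2 of 3 points and the seven-analyte panel at 1 of 3. Week 8 covers 1 of 7 analytes.

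**Step 2. Is the Schedule row being read correctly?** Its header is broken in the extracted text. The HCV RNA row, read with the same column order, gives screening, Week 4, Week 12 and Week 24, which agrees with the visit lists. The Week 4 and Week 8 liver-test entries are also confirmed by the plain-text lists. The finding does not depend on the table layout.

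**Step 3. Length of the gap if only the lists and Schedule are followed.**

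- Baseline to first scheduled ALT: 56 - 0 = 56 days.
- Ratio to the stated interval: 56/28 = 2.0.
- With the Week 8 window: 49/28 = 1.75 to 63/28 = 2.25.
- With the same window applied to a Week 4 test (Day 21 to 35): late against late, 63/35 = 1.8; early against early, 49/21 = 2.33.
- Share of the treatment course: 56/84 = 67%.

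The gap is about double on any of these comparisons.

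**Step 4. Does anything else supply the Week 4 test?** No visit-list entry, Schedule row or Schedule footnote adds a liver test for participants with prior HBV infection. The lists do mark other restricted tests where they fall due: pregnancy tests for females of childbearing potential, and finger-stick tests at sub-study sites.

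**The case against.** The strongest reply is that nothing is contradicted. The lists cover all participants, and the HBV paragraph follows them under its own heading, in mandatory wording, as an extra rule for a subgroup. A site can obey both by doing the list and adding 4-weekly LFTs where prior HBV infection is found. HBV DNA testing, required by the same paragraph, also appears in no list or Schedule row, so the protocol does state some HBV procedures in text only.

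This reading is tenable, and it turns the defect into an omission. It does not remove it. HBV DNA testing is triggered by events and has no fixed visit, so its absence from a visit schedule is natural. A 4-weekly test falls on scheduled visits, and at one of them the lists and Schedule are silent. The reading also leaves open what LFTs means at Week 8.

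Three further objections bear on size:

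- **Week 8 is the lesser part.** ALT is the only analyte named as a trigger, and it is measured at Week 8. This stands: Week 4 carries the consequence, and Week 8 needs only clarification.
- **The upper ratio of 2.25 sets a windowed visit against an unwindowed interval.** This is fair, and the full range is given above. The nominal ratio of 2.0 is the one to use. All the ratios assume a site that does not act on the HBV paragraph.
- **The exposure is narrow.** People with current HBV infection are excluded, symptoms and signs are a separate trigger, and sites are told to explain them: "Patients should be encouraged to report any signs or symptoms". This stands and limits the point to ALT rises without symptoms before Week 8.

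**Conclusion.** The concern holds. The HBV paragraph states liver tests every 4 weeks on treatment. The visit lists and Schedule provide none at Week 4, ALT alone at Week 8 and the full panel only at Week 12. A site following the lists and Schedule would have no scheduled ALT for 56 days after Baseline, against a stated 28, and so would lack the only laboratory trigger for HBV DNA testing over the first two-thirds of treatment.

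This rests on two assumptions: that the 4-weekly count starts at Baseline, and that the site works from the lists or Schedule without adding the test from the HBV paragraph. The documents do not say how many participants will have prior HBV infection, so the number affected cannot be estimated.

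It is an internal inconsistency in safety monitoring that should be fixed. It does not bear on the SVR12 estimate, the reinfection rate or their sample-size figures. No view is taken here on which monitoring frequency or panel is right.

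**What to change.** Reconcile the HBV reactivation paragraph, the Week 4 and Week 8 lists in Section 6.1 and the liver-test row of the Schedule, so that all name the same tests at the same on-treatment visits for participants with prior HBV infection. A Schedule footnote for that subgroup, with a matching entry in the visit lists, would do this. In the HBV paragraph, state whether LFTs means the seven-analyte panel or ALT alone. The clinical team decides which version applies.

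The cost is a document edit. If the 4-weekly text is kept, it adds one local laboratory test at Week 4 for this subgroup, at a visit where blood is already taken for HCV RNA and research plasma. It also adds a fuller panel at Week 8 if the defined LFT panel is what is meant.
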